# **Mastectomy Flap Temperature and Clinical Implications**

Wake Forest Baptist Comprehensive Cancer Center

WFBCCC # 74222

**Mastectomy Flap Temperature and Clinical Implications**

Wake Forest Baptist Comprehensive Cancer Center

WFBCCC # 74222

**SCHEMA**

## Mastectomy Flap Temperature and Clinical Implications

Wake Forest Baptist Comprehensive Cancer Center

WFBCCC # 74222

### 1.0 Introduction and Background

Breast cancer is the most common cancer diagnosis of women in the United States, making up 25% of all cancer diagnoses. Among those undergoing surgical intervention, 50% have a mastectomy. Within this group of mastectomy patients, up to 50% opt for breast reconstruction. The most recent surgical trend data from the American Society of Plastic Surgeons shows that almost 90,000 breast reconstructions in the United States were implant-based in 2019, making up approximately 80% of all breast reconstructions. Along with the upward trend in implant-based breast reconstruction, there remain high rates of surgical complications. The rate of surgical site infections is higher in implant-based reconstruction as compared to autologous reconstruction. The implant-based reconstruction infection rates range from approximately 6-28%, while the infection rate for autologous reconstruction is 5% and 0.1-1.5% for breast augmentation. The sequela of surgical site infection can place a significant burden on the patient and healthcare system and can even delay oncologic care in some cases. Numerous protocols and anecdotally based methods are often applied in efforts to reduce surgical site infection. Despite these attempts, there remains a large gap in evidence-based medicine on how to successfully decrease risk of surgical site infection in implant-based breast reconstruction.

Clinicians often note that both intraoperatively, and months postoperatively, mastectomy flaps are clinically cool to the touch, but mastectomy flap temperature has not been objectively studied. The importance of maintaining normothermia during surgery has been well established in both anesthesia and surgical specialties literature over the past twenty years. The combinations of impaired thermoregulatory control from the anesthesia and exposure to cool operating rooms makes most surgical patients hypothermic (defined by anesthesia practitioners as being less than or equal to 36 degrees celsius.) Wound temperature is heavily reliant on, and correlated with, core body temperature, as the wound temperature is higher in normothermic patients than in hypothermic patients. The clinical impact of this has most markedly been observed in the colorectal specialty in which a study found that patients with mild perioperative hypothermia had three times as many surgical-wound infections as the normothermic patients. As stated above, implant-based reconstruction after mastectomy consistently has higher rates of infection than other implant based procedures or even autologous breast reconstruction. This is often attributed to the decreased mastectomy flap perfusion that becomes solely reliant upon the subdermal plexus after a total mastectomy ultimately leading to impaired blood flow and subsequent impairment in immune function.

Hypothermia causes vasoconstriction leading to immune dysfunction among t-cell-mediated antibody production, chemotaxis, phagocytosis of granulocytes, motility of macrophages, and non-specific oxidative bacterial killing by neutrophils. The decrease in killing by neutrophils occurs due to decreased blood flow, in turn decreasing the oxygen tension of mastectomy flaps. This causes a decreased production of both oxygen and nitrous free radicals, which is an oxygen-dependent process. This oxidative killing process is responsible for many gram positive organisms such as *Staphylococcus aureus*, which is the most frequently isolated organism in breast implant infections. Hypothermia and impaired blood flow in the first few hours of the case can render preoperative antibiotics less effective or in some cases ineffective. Furthermore, after surgery core hypothermia can take up to five hours to resolve, which leads to bacterial fixation and risk for infection. An animal *in vivo* study demonstrated reduced resistance to test infection suggesting that temperature plays a vital role in immune function.

## Mastectomy Flap Temperature and Clinical Implications

Wake Forest Baptist Comprehensive Cancer Center

WFBCCC # 74222

The blood flow has also been described in the setting of temperature dependent blood flow in flaps. Most surgeons assess the flaps subjectively by observing temperature, capillary refill and overall appearance of the flap. While often utilized, it is not reliable or reproducible to rely on the intuition and experience of the surgeon. In an animal study, it was found that skin perfusion often increases in the first 24-48 hours after surgery. The researchers found that if intraoperatively the flap is heated to 42 degrees Celsius it mimics the microcirculatory environment encountered at 24-48 hours post-surgery. The warming of the flap can stave off the deleterious effects of the vasoconstriction. Vasoconstriction has been found to create a hyperadrenergic state causing further vasoconstriction, perpetuating the cycle of hypoperfusion and lower temperatures. The lower temperatures have been found to inhibit nitrous oxide secretion causing overexpression of alpha-2c adrenergic receptors which amplifies the vasoconstrictive effects. In addition, thermoregulatory vasoconstriction significantly decreases subcutaneous oxygen tension. The incidence of wound infections correlates with subcutaneous oxygen tension.

Given the increasing quantity of literature that concludes that core temperature is an independent risk factor for increased complications there has been an attempt to control this by preconditioning the mastectomy flaps. Five to thirty percent of mastectomy skin flap necrosis is often cited in the literature. While in its infancy, the handful of studies that have attempted this intervention have found promising outcomes. One review article examined the concept of thermal preconditioning which was defined as "local or systemic supraphysiological heating of an organism or specific organ before an environmental insult." It has been established that through heat exposure there is an increase in heat shock proteins (HSP). Specifically, HSP-32 can catalyze hemoglobin to biliverdin and iron with a byproduct of this reaction being the local release of carbon monoxide. Carbon monoxide is a potent vasodilator that causes an increase in vascularity to the specific preconditioned area. HSP-70 is also suspected to play a role in vasodilation through inducing production of nitrogen oxide synthase (iNOS). Protective effects of HSP and preconditioning has been demonstrated in multiple other organs like kidneys, bone, heart and liver. This physiologic reaction was examined in a randomized control trial through local supraphysiologic heating of breasts that were to undergo mastectomy the following day. A heat source of 43 degrees Celsius was applied for 30 minutes 3 times with a 30-minute rest between the repetitions. It was found that those who did not undergo preconditioning had 35% necrosis rate of mastectomy flaps, while those who did undergo preconditioning experienced 26% necrosis rate of mastectomy flaps.

To date there has been no study that has examined the feasibility of objectively quantifying the temperature of mastectomy flaps, or that has studied the relation between flap temperatures and core body temperature. This pilot study seeks to establish foundational evidence related to the feasibility of measuring temperatures of mastectomy flaps and to quantify the relation between flap and core temperatures. Specifically, we hypothesize that 1. we will be able to obtain consent from at least 60% of women undergoing therapeutic or prophylactic mastectomy (unilateral or bilateral, with reconstruction) to obtain flap temperatures intraoperatively, both pre- and post-mastectomy (note that core body temperature is measured continually as a usual aspect of intraoperative procedure, and thus does not require specific additional consent); 2. we will be able to successfully measure flap temperatures in 4 quadrants of relevant breast tissue (one or both breasts, depending on unilateral vs bilateral surgery) at each time point on at least 90% of those who do consent; and 3. average mastectomy flap temperatures will be significantly lower than core body temperature in this pilot sample.

## **Mastectomy Flap Temperature and Clinical Implications**

Wake Forest Baptist Comprehensive Cancer Center

WFBCCC # 74222

Additionally, we will explore the relation between average mastectomy flap temperature and number and degree of post-surgical complications for up to 90 days post-surgery, to examine whether patients with cooler mastectomy flaps intraoperatively have increased surgical complications compared to patients with warmer flaps. While there is a possibility that the presence or absence of cancer can affect surgical complication rates, we do plan to include patients undergoing both therapeutic and prophylactic mastectomy in this study. When performing data analysis, complications are recorded by breast rather than by patient allowing us to note which breasts undergo mastectomy for therapeutic reasons and which are prophylactic.

If we are successful in showing feasibility in our primary objectives, we hope that these pilot data will ultimately aid in future, large interventions designed to warm or precondition mastectomy flaps in efforts to optimize surgical outcomes for implant based breast reconstruction surgeries.

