**Table 1: Data Points to be Collected**

Preoperative	

- MRN

- Age

- BMI

- Smoking status

- Diabetes Mellitus

- Neoadjuvant radiation

- Neoadjuvant Chemotherapy

- Tumor type and stage

Intraoperative	

- Mastectomy weight

- Size of tissue expander or implant placed

- Number of drains placed

- Temperature collection:

- Pre-mastectomy - core temp and flap temp in 4 quadrants

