### **6.3 Data Analyses**

This study will provide quantitative data on consent (proportion of all eligible patients approached who consent to having flap temperatures measured intra-operatively), and on ability to successfully measure all 12 flap temperatures (per breast) on patients who have consented.

We will calculate 95% confidence intervals for each of the above feasibility measures to determine the range of estimates that are consistent with our data. We will use one-sample tests of binomial proportions to compare the consent and successful measurement proportions to the hypothesized values of 60% and 90%, respectively.

We will examine intra-individual variability in flap temperature measurements by quadrant and by breast; we expect these sources of potential variability to be weak, controlling for time point of measurement (pre vs post mastectomy vs pre-implantation). We will derive average flap temperatures for each of the three time points separately. We will compare average flap temperatures at each of the three time points during surgery to average core body temperature at that time, using paired t-tests for the differences in means in a single sample. Our hypothesis is that, across all three time points, average flap temperatures will be lower than average core body temperatures, and that as time goes on during surgery, from pre- to post-mastectomy to pre-implantation, we expect average flap temperatures will be lower than average core body temperatures by a larger degree, as we expect flap temperatures to cool more quickly during surgery than overall body temperature.

In our exploratory analyses, we will document the occurrence and major and minor wound/surgical complications over the 90-day period following surgery and will examine whether there is a relation between the number of such complications per patient and 1. the patient's magnitude of difference between average flap temperatures and core body temperatures, and 2. the patient's absolute average flap temperatures .

.

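### Section 1.0 relies on by-breast recording to separate therapeutic from prophylactic mastectomy, but the exploratory analysis in Section 6.3 is per patient and does not use it

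*Combined protocol and SAP*

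**What the plan says.** The closing paragraphs of Section 1.0 concede that "there is a possibility that the presence or absence of cancer can affect surgical complication rates" and nevertheless enrol women having therapeutic and women having prophylactic surgery. The reason given is the unit of recording: "When performing data analysis, complications are recorded by breast rather than by patient". Section 1.0 presents this choice of unit as "allowing us to note which breasts undergo mastectomy for therapeutic reasons and which are prophylactic".

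Section 6.3 sets out the exploratory analysis. It asks "whether there is a relation between the number of such complications per patient" and two exposures, both defined for the patient: the "magnitude of difference between average flap temperatures and core body temperatures" and her "absolute average flap temperatures". It names no covariate, stratum, subgroup or by-breast model for indication. Section 6.1 adds only that complications will be described as frequencies.

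Table 1 has no entry for side or for therapeutic versus prophylactic indication, and does not say that complications are captured per breast. The nearest item is "Tumor type and stage". Section 5.1 says that the list in Table 1 is not exhaustive.

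**The concern.** Section 1.0 offers one safeguard for mixing the two indications, and Section 6.3 as written sets it aside. A woman with one cancer-bearing and one prophylactic breast contributes a single averaged temperature and a single pooled count. She cannot be placed in either indication group, and the comparison between her two breasts is lost. The pooled count also rises with the number of breasts operated on, so it mixes two things unrelated to temperature.

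What is at stake is how the exploratory result can be read. Section 1.0 hopes that the pilot data will help later work on warming or preconditioning flaps. If indication is related to both temperature and risk, a relation seen or not seen in the per-patient analysis could not be attributed to flap temperature, and the planned output would not show the reader why.

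**Working it through.** **Setting.** The plan gives no figure for this relation. The relevant number is the expected analysis set in Section 6.2: 60% × 30 = 18 women, hence 18 to 36 breasts. The stated precision there does reproduce: the exact (Clopper-Pearson) 95% interval for 18/30 is 40.6% to 77.3%, and 60 − 40.6 = 19.4 points. It does not bear on this point.

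**Assumptions (none is in the documents).** Case mix: 40% unilateral therapeutic (A), 40% bilateral with one breast of each kind (B), 20% bilateral prophylactic (C). Temperature SD is 0.7 °C between women and 0.5 °C between breasts within a woman. Therapeutic flaps are cooler by d = 0.5 or 1.0 °C. Complication risk per breast is 35% therapeutic against 20% or 10% prophylactic. Temperature has no effect on complications.

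**Expected count per patient.**
- 35% v 20%: A 0.35; B 0.35 + 0.20 = 0.55; C 0.40. Mean 0.4×0.35 + 0.4×0.55 + 0.2×0.40 = 0.44.
- 35% v 10%: A 0.35; B 0.45; C 0.20. Mean 0.36.

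Mean temperature shift is −d for A, −d/2 for B and 0 for C. The coolest group, A, has only one breast at risk.

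**Planned per-patient relation, d = 1.0.**
- Mean shift: 0.4×(−1) + 0.4×(−0.5) = −0.6.
- Covariance of shift and count at 35% v 20%: (−0.14 − 0.11) − (−0.6×0.44) = +0.014. At 35% v 10%: (−0.14 − 0.09) − (−0.6×0.36) = −0.014. The sign changes.
- Variance of patient-average temperature: 0.49 + (0.4×0.25 + 0.6×0.125) + (0.4×1 + 0.4×0.25 − 0.36) = 0.805.
- Slope: 0.014/0.805 = 0.0174 complications per °C. Relative to the mean this is 0.0174/0.44 = 0.040 or 0.0174/0.36 = 0.048.
- Rate ratio per °C cooler: exp(−0.040) = 0.96, or exp(0.048) = 1.05.

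**Allowing for breasts at risk, d = 1.0.** Weight each woman by her number of breasts (A 0.4, B 0.8, C 0.4; total 1.6).
- At 35% v 10% the risks per breast are 0.35, 0.225 and 0.10, mean 0.225. Mean shift is −0.5.
- Covariance: (−0.14 − 0.09)/1.6 + 0.5×0.225 = −0.031.
- Variance: 0.49 + 0.156 + 0.125 = 0.771.
- Rate ratio per °C cooler: exp(0.031/0.771/0.225), about 1.20.

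**All four settings.** A simulation of 600,000 women per setting, with Poisson regression and log number of breasts as offset in the last column, agrees with this arithmetic:

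| Risk, therapeutic v prophylactic | Therapeutic cooler by | Planned per-patient rate ratio per °C cooler | With breasts at risk as offset |
|---|---|---|---|
| 35% v 20% | 0.5 °C | 0.98 | 1.05 |
| 35% v 20% | 1.0 °C | 0.96 | 1.09 |
| 35% v 10% | 0.5 °C | 1.03 | 1.11 |
| 35% v 10% | 1.0 °C | 1.05 | 1.20 |

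The lowest offset figure falls at 1.05 or 1.06 across repeat runs. With d = 0 every ratio is 1.00.

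**At the expected size.** With n = 18, a rank correlation of count on temperature rejects in about 5% of simulated studies, its nominal level, so noise dominates any bias.

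**The case against.** Several counter-arguments carry weight.

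- **Confounding is not shown.** A reader might infer that the plan will make cooler flaps look more prone to complications. That needs therapeutic flaps to be cooler, which the documents never say; they mention only the link from cancer to complications, and only as a possibility. In the 35% v 20% settings the planned analysis even errs the other way. This stands.
- **Larger figures belong to a different analysis.** Under the same assumptions, an unadjusted breast-level logistic model gives odds ratios of about 1.13 to 1.45 per °C cooler, returning to about 1.0 once indication is added. It would be tempting to quote these, but Section 6.3 plans no such model.
- **Data capture is not excluded.** Section 5.1 leaves Table 1 open, Section 1.0 commits to noting indication, neoadjuvant radiation and chemotherapy are listed, and Section 6.3 looks at temperature variability by breast. A reader might infer that indication will not be recorded; the documents do not support that. What stands is that side and indication are not named in the list of data points.
- **Section 1.0 promises only to note indication,** and it also words its question in terms of patients. This is true, but a note that no analysis uses does not answer the concern that it was offered to answer.
- **The sample is small.** A clustered model with an indication term on about 18 women would be unstable. This limits the remedy, not the need to reconcile the two sections.

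**Conclusion.** The two sections do not fit together. Section 1.0 relies on by-breast recording to tell the indications apart, while Section 6.3 pools to the patient and leaves indication out. As written, the complication count mixes indication with one or two breasts at risk.

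The size and direction of any bias cannot be settled from the documents. Under the stated assumptions it is small for the planned analysis (rate ratio about 0.96 to 1.05 per °C cooler), somewhat larger once breasts at risk are allowed for (about 1.05 to 1.20), and absent if therapeutic flaps are not cooler. The fault is therefore a safeguard that is stated but not used, leaving a result that is hard to interpret. It is not a demonstrated false association.

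The consequence is confined to the exploratory objective. The feasibility decision rests on consent and measurement success. Section 6.2 ties the power of a later study to flap-core differences, so a reader should not infer that this association would drive its sample size.

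**What to change.** In Section 6.3, make the breast the unit of the exploratory relation. Relate each breast's own average flap temperature, and its own difference from core temperature, to that breast's complications. Show results separately for therapeutic and prophylactic breasts, and allow for two breasts from one woman (for example GEE or a random intercept, if a model is fitted at all). Keep the per-patient summary as description, and label the whole analysis descriptive because about 18 women are expected.

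In Table 1, name side, indication, side of any radiation, and complications for each breast, so that the commitment in Section 1.0 can be carried out.

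The cost is a few fields taken from the chart and a short edit to Section 6.3. The drawback is less stable estimates if an adjusted model is fitted in so small a sample; tabulation by indication avoids most of that.

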## **2.0 Objectives**

### **2.1 Primary Objective(s)**

- 2.1.1 Quantify the proportion of eligible women approached who consent to intraoperative (pre and post mastectomy) measurement of mastectomy flap temperatures in each of 4 quadrants of each relevant breast (i.e., unilateral or bilateral procedure).
- 2.1.2 Quantify the proportion of patients upon whom the surgical team is able to obtain intraoperative flap measurements from each of 4 quadrants on each relevant breast pre- and post-mastectomy and pre-implant.

### **2.2 Secondary Objective(s)**

- 2.2.1 To measure mastectomy flap temperatures in 4 quadrants pre-mastectomy, following mastectomy, and pre-implant, and compare average flap temperature to average core body temperature.

### **2.3 Exploratory Objective(s)**

- 2.3.1 Quantify relationship between flap temperatures and incidence of mastectomy surgical complications within 90 days of surgery.

## **3.0 Patient Selection**

### **3.1 Inclusion Criteria**

- 3.1.1 Scheduled for unilateral or bilateral mastectomy with implant based breast reconstruction within the Wake Forest Baptist Health System.
- 3.1.2 Aged 18 or older.

## **Mastectomy Flap Temperature and Clinical Implications**

Wake Forest Baptist Comprehensive Cancer Center

WFBCCC # 74222

3.1.3 Ability to understand an IRB-approved informed consent document (either directly or via a legally authorized representative).

### **3.2 Exclusion Criteria**

3.2.1 Those who are male.

### **3.3 Inclusion of Women and Minorities**

Women of all races and ethnicities who meet the above-described eligibility criteria are eligible to participate in this study. Because they do not get implant-based reconstruction (and have a comparatively low risk of breast cancer) men will be excluded from this study.

The study consent form will also be provided in Spanish for Spanish-speaking participants.

## **Mastectomy Flap Temperature and Clinical Implications**

Wake Forest Baptist Comprehensive Cancer Center

WFBCCC # 74222

## **4.0 Study Outcomes and Study Measures**

### **4.1 Primary Outcomes**

5.1.1 The proportion of eligible women who consent to having mastectomy flap temperatures measured during surgery will be computed by dividing the total number of eligible women screened by the number of these women who consent. We will compute a 95% confidence interval around this proportion.

5.1.2 We will compute the proportion who successfully have all relevant flap temperatures measured (this will either be 12 or 24 total expected flap temperatures: 4 quadrants, at three time points- pre and post-mastectomy and pre-implant placement; one or both breasts), and we will compute a 95% confidence interval around this proportion.

### **4.2 Secondary Outcome**

- Mastectomy flap temperatures will be measured using a 22 gauge myocardial temperature sensor (Smiths Medical). Temperatures will be recorded in degrees Celsius. Core body temperature will also be collected.

### **4.3 Exploratory Outcome**

Mastectomy flap compromise/wound breakdown (major vs. minor complication) will be assessed over 90 days following surgery. We will document the following through chart review including but not limited to infection, ischemia, seroma, hematoma, and wound dehiscence.

